Detailed methodology for summary and statistical analyses of the data collected in this study will be documented in a statistical analysis plan (SAP) that will be maintained by the sponsor. The primary endpoint of the study is the change from baseline in the simplified disease activity index (SDAI) at 12 weeks. The primary analyses will include: Analysis of Covariance (ANCOVA) models adjusting for SDAI baseline value and Bayesian analyses of posterior distributions of the SDAI scores and placebo adjusted change from baseline. Missing values due to a subject dropping from the study for lack of efficacy or adverse event, will be handled by setting the SDAI score to nonresponsive (baseline observation carried

090177e190fc2bd0Approved On: 27-May-2019 05:59 (GMT)

forward, BOCF). Missing values that occur while the subject is still enrolled (eg, due to a protocol deviation where the data were not collected), will be handled by the method of last observation carried forward (LOCF). The most recent data on each SDAI domain will be used for calculating the missing SDAI score. The statistical analysis will not include comparison between the PF-06650833 and tofacitinib arms.

The indicator of prior exposure and inadequate response to anti-TNF treatment will be used as a stratification variable for randomization. Randomization will be stratified to achieve equal proportion of anti-TNF inadequate responders in all arms.

[figure not shown]
At least one interim analysis (IA) for futility may be performed. The final number and timing of the IA(s) will be defined by the sponsor, but preliminarily one may be conducted at approximately 6 months after the randomization of the first subject and/or after at least 50% of the planned subjects, ie, approximately 100 subjects, have completed the twelve week active treatment phase.

SCHEDULE OF ACTIVITIES

The schedule of activities table provides an overview of the protocol visits and procedures. Refer to the [STUDY PROCEDURES](#) and [ASSESSMENTS](#) sections of the protocol for detailed information on each procedure and assessment required for compliance with the protocol. The investigator may schedule visits (unplanned visits) in addition to those listed on the schedule of activities, in order to conduct evaluations or assessments required to protect the well-being of the subject.

[figure not shown]
Protocol Activity	Screening	Treatment Period								FU	FU/EOS	EW ^b
	1	2	3	4	5	6	7	8	9	10		

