Tender/Painful Joint Count (68)	X	X		X		X		X		X	X	
Swollen Joint Count (66)	X	X		X		X		X		X	X	
Patient Assessment of Arthritis Pain (PAAP) VAS		X		X		X		X		X	X	
Patient Global Assessment (PtGA) of Arthritis VAS		X		X		X		X		X	X	
Physician Global Assessment (PhGA) of Arthritis ^f		X		X		X		X		X	X	
Health Assessment Questionnaire – Disability Index (HAQ-DI)		X		X		X		X		X	X	
SF-36 Version 2 (Acute)		X						X		X	X	
FACIT-Fatigue		X						X		X	X	
EQ-5D-3L		X						X		X	X	
Log into IRT system	X	X	X	X		X				X	X	
Investigational Product Dispensing		X	X ^w	X		X						
Randomization (after all screening procedures are complete and reviewed) ^s		X										

090177e190fc2bd0Approved\Approved On: 27-May-2019 05:59 (GMT)

Protocol Activity	Screening	Treatment Period								FU	FU/EOS	EW ^b
Visit Identifier	1	2	3	4	5	6	7	8	9	10		
Study Day/Week ^a	Days -28 to 0	Week 0	Week 1	Week 4	Week 6	Week 8	Week 10	Week 12	Week 14	Week 16		
		Day 1/ Baseline	Day 8	Day 29	Day 43	Day 57	Day 71	Day 85	Day 99	Day 113		
Visit Window	Days -28 to 0	±2 Days based on Week 0/Day 1 visit										
Administration of PF-06650833, Placebo or Tofacitinib ^t		X	X	X	X	X	X	X				
Review of subject diary (review of subject dosing record), IP accountability and compliance check throughout the study ^u		X	X	X	X	X	X	X			X	
Dispensing of subject diary		X	X	X	X	X	X					
Serious and non-serious adverse event monitoring	X	→	→	→	→	→	→	→	→	X	X	
Prior/Concomitant Medication & Treatments		X	→	→	→	→	→	→	→	X	X	
Discharge from the study										X	X	

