Abbreviations: → = ongoing/continuous event; ACR = American College of Rheumatology; ACPA = Anti CCP Antibodies; DNA = deoxyribonucleic acid; ECG = electrocardiogram; eGFR = estimated glomerular filtration rate; EOS = end of study; EW = early withdrawal; ESR = Erythrocyte Sedimentation Rate; EQ-5D-3L = European Quality of Life – 5 Dimensions 3 Level; CCI FACIT-Fatigue Scale = Functional Assessment of Chronic Illness Therapy fatigue scale; FSH = follicle stimulating hormone; FU = Follow-up; HAQ-DI = Health Assessment Questionnaire – Disability Index; HBcAb = hepatitis B core antibody; HBsAg = hepatitis B surface antigen; HBsAb = hepatitis B surface antibody; HBcAb = hepatitis B core antibody; HCVAb = hepatitis C antibody; HIV = human immunodeficiency virus; hsCRP = high-sensitivity C-reactive protein; IgA, G, M, E = Immunoglobulin of the A, G, M, E isotypes; IGRA = interferon-gamma release assay; IP = investigational product; IRB = institutional review board; CCI PAAP = Patient Assessment of Arthritis Pain; PtGA = patient global assessment; PhGA = Physician Global Assessment; WONCBP = women of non-childbearing potential

- Visits should occur when scheduled, within the time window indicated in the column headings. On study drug dosing days, assessments (including joint counts and questionnaires), and pre-dose blood collections are to be performed prior to dosing unless otherwise stated. Patient reported assessments, including PtGA and PAAP VAS measures and HAQ-DI questionnaires, should be performed prior to any other assessments. Additional unscheduled assessments should be performed as clinically indicated.
- Any subject who prematurely withdraws from the treatment period should undergo the procedures for an early withdrawal visit and return for follow up visits as medically indicated in the opinion of the PI.
- RA medications taken before and after informed consent are signed.

- d. Vital Signs include: sitting blood pressure, pulse, and temperature (oral, temporal, tympanic or axillary same throughout the study), measured after approximately 5 minutes of rest.
- e. Complete physical exam (PE) of major body systems Additional brief PE may be performed during the study at the investigator's discretion.
- f. An ECG may be performed at other times, at the discretion of the Investigator if there were findings during a previous examination or in the case of a new/open adverse event (AE).

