6.4. Subject Withdrawal/Early Termination Visit

If a patient has any clinically significant, treatment-emergent, abnormalities at the conclusion of the study, the Pfizer Medical Monitor (or designated representative) should be notified and every effort should be made to arrange follow-up evaluations at appropriate intervals to document the course of the abnormality. All abnormal laboratory events of clinical significance should be followed until the laboratory values have returned to normal or baseline levels or is otherwise considered stable by the Principal Investigator and the Pfizer Medical Monitor.

Patients may withdraw from the study at any time at their own request, or they may be withdrawn at any time at the discretion of the investigator or sponsor for safety (see also the [Withdrawal From the Study Due to Adverse Events](#) section) or behavioral reasons, or the inability of the subject to comply with the protocol-required schedule of study visits or procedures at a given study site. If a patient does not return for a scheduled visit, every effort should be made to contact the patient. All attempts to contact the subject and information received during contact attempts must be documented in the subject's medical record). In any circumstance, every effort should be made to document patient outcome, if possible. The investigator should inquire about the reason for withdrawal; request that the patient return all unused investigational product(s); request that the patient return for a final visit, if applicable, and follow-up with the patient regarding any unresolved adverse events.

If the patient withdraws from the study, and also withdraws consent for disclosure of future information, no further evaluations should be performed, and no additional data should be collected. The sponsor may retain and continue to use any data collected before such withdrawal of consent.

Procedures that will be performed on early withdrawal visit include with subject consent:

- ACR/DAS Assessments: Tender/Painful Joint Counts (68), Swollen Joint Count (66), Patient Assessment of Arthritis Pain, Patient Global Assessment of Arthritis, Physician Global Assessment of Arthritis, Health Assessment Questionnaire – Disability Index (HAQ-DI);

- Collect additional PROs: SF-36 Version 2 (Acute), FACIT-fatigue scale, EQ-5D-3L;

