- Review concomitant Medication and Treatments (RA and non RA): Current and prior medications (noting exclusions and required DMARD restrictions) taken with reasons and should include dose/duration;
- Vital signs: sitting blood pressure, pulse, and temperature (tympanic, oral, axillary or temporal);
- Perform targeted physical Examination;
- 12-lead electrocardiogram;
- Collect blood samples for chemistry (including hsCRP) and hematology laboratory assessments;
- Collect blood sample for local ESR assessment;
- Collect blood sample for ACPA;
- Collect blood sample for immunoglobulin Ig (IgA, IgM, IgG, IgE) analyses;
- CCI [REDACTED]
- Confirm proper contraception is being used;
- Collect urine sample for central laboratory urinalysis and urine microscopy;
- Collect urine for local urine pregnancy testing (women of childbearing potential, only);
- CCI [REDACTED]
- CCI [REDACTED]
- CCI [REDACTED]
- CCI [REDACTED]
- Review of the diary for compliance with daily diary completion (and provide subject retraining as required), IP accountability and compliance check through the study;
- Serious and nonserious adverse events monitoring;

090177e190fc2bd0\Approved\Approved On: 27-May-2019 05:59 (GMT)

- Log into IRT system and register the subject's status as discontinued and discharge the subject from the study.

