8.1.2. Eliciting Adverse Event Information

The investigator is to record on the CRF all directly observed AEs and all AEs spontaneously reported by the study subject. In addition, each study subject will be questioned about the occurrence of AEs in a non-leading manner.

8.1.3. Withdrawal From the Study Due to Adverse Events (see Also the [Subject Withdrawal Section](#))

Withdrawal due to AEs should be distinguished from withdrawal due to other causes, according to the definition of AE noted below, and recorded on the CRF.

When a subject withdraws from the study because of an SAE, the SAE must be recorded on the CRF and reported, as appropriate, on the CT SAE Report Form, in accordance with the [Requirements](#) section above.

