8.1.4. Time Period for Collecting AE/SAE Information

The time period for actively eliciting and collecting AEs and SAEs (“active collection period”) for each subject begins from the time the subject provides informed consent, which is obtained before the subject’s participation in the study (ie, before undergoing any study-related procedure and/or receiving investigational product), through and including a minimum of 28 calendar days after the last administration of the investigational product.

For subjects who are screen failures, the active collection period ends when screen failure status is determined.

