8.1.4.1. Reporting SAEs to Pfizer Safety

All SAEs occurring in a subject during the active collection period are reported to Pfizer Safety on the CT SAE Report Form.

SAEs occurring in a subject after the active collection period has ended are reported to Pfizer Safety if the investigator becomes aware of them; at a minimum, all SAEs that the investigator believes have at least a reasonable possibility of being related to investigational product must be reported to Pfizer Safety.

Follow up by the investigator continues throughout and after the active collection period and until the event or its sequelae resolve or stabilize at a level acceptable to the investigator, and Pfizer concurs with that assessment.

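### Subjects withdrawn from the study are discharged at the early withdrawal visit, and no scheduled step asks them about new adverse events up to the 28 days after last dose that Protocol 8.1.4 requires

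*Protocol*

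**What the plan says.** Protocol 8.1.4 sets an active collection period for every subject. It starts at consent and runs "through and including a minimum of 28 calendar days after the last administration of the investigational product". The only exception given there is screen failures. Section 8.1.2 makes the questioning active: "each study subject will be questioned about the occurrence of AEs in a non-leading manner".

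For a subject withdrawn from the study, 6.4 lists the EW procedures. AE monitoring is among them, and the last step is an entry in the interactive response technology (IRT) system: "status as discontinued and discharge the subject from the study". The Schedule of Activities agrees. Its row "Discharge from the study" is marked at Visit 10 and at EW.

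After that, footnote b of the Schedule has the subject "return for follow up visits as medically indicated in the opinion of the PI". The Schedule's introduction adds an option: "The investigator may schedule visits (unplanned visits) in addition to those listed on the schedule of activities". Section 6.4 asks the investigator to "follow-up with the patient regarding any unresolved adverse events". Section 8.1.4.1, on SAE reporting, says: "Follow up by the investigator continues throughout and after the active collection period". Section 7.7 attaches follow-up or retesting to some laboratory withdrawals.

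Section 6.4.1 keeps subjects who ask only to stop treatment in the study with protocol follow-up, unless they withdraw consent to contact.

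**The concern.** Section 8 sets a duty that lasts to day 28 after the last dose. Section 6 and the Schedule give the site a withdrawal checklist that can finish well before then. A site that follows the checklist exactly discharges the subject with part of the 28 days still to run and nothing booked. Completers, by contrast, have AE monitoring scheduled at Weeks 14 and 16.

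What may be missed is a new AE that starts after the EW visit but within 28 days of the last dose, in a subject nobody asks. Some of these subjects leave for safety reasons: 6.3, 7.6.2 and 7.7 discontinue subjects from the study itself, not only from drug, for events such as kidney injury, liver enzyme elevation, cytopenia and serious infection. Safety is a secondary objective, and SAP 6.7.1 reports between-treatment differences in AE percentages.

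**Working it through.** **1. The plan's own figure, for completers.** The last dose is given in clinic at Visit 8 (Day 85) and discharge is at Visit 10 (Day 113). 113 − 85 = 28 days, so on target days the schedule delivers the minimum in 8.1.4.

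Both visits have a ±2-day window anchored on Day 1 (Schedule; 5.4.2). The in-window gap therefore runs from 111 − 87 = 24 to 115 − 83 = 32 days. For a last dose on Days 83, 84, 85, 86 or 87, adding 28 gives Days 111, 112, 113, 114 or 115. Every one lies inside the Visit 10 window of Days 111 to 115, so a compliant date is always available.

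**2. Subjects withdrawn from the study.** The provisions that could supply a contact by day 28 are:

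| Provision | What it supplies | Fixed question about new AEs to day 28? |
|---|---|---|
| 6.4 and Schedule, EW visit | AE monitoring at the visit, then discharge | No, unless the visit itself falls that late |
| Schedule, footnote b | Return visits at the investigator's discretion | No |
| Schedule, introduction | Optional unplanned visits | No |
| 6.4 | Follow-up of significant abnormalities and unresolved AEs; effort to document outcome | No; no day is set |
| 7.7 | Follow-up to resolution for haemoglobin, platelet, neutrophil and lymphocyte withdrawals; creatinine retesting to within 10% of pretreatment | No; tied to the known abnormality, may end earlier |
| 8.1.4.1 | Follow-up of an event already identified | No |
| 6.4.1 | Full protocol follow-up | Not for this group; covers those who stop treatment and stay in |

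The number of fixed AE contacts after the EW visit is zero.

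**3. Uncovered time per subject.** Uncovered days = 28 − (days from last dose to EW visit). The protocol fixes no day for the EW visit, so the lags below are assumptions:

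- lag 0: 28 days
- lag 2: 26 days
- lag 8: 20 days
- lag 14: 14 days

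A subject withdrawn under 6.3 for interrupting medication for more than 7 days, and still off drug, is at least 8 days past the last dose. The shortfall is then at most 28 − 8 = 20 days.

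**4. How many subjects.** Sections 3 and 9.1 plan about 230 enrolled for about 198 completers of dosing. 230 − 198 = 32, which is 32/230 = 13.9%. The stated 15% of 230 is 34.5. (198/0.85 = 232.9, consistent with approximately 230.) So planned non-completers number about 32 to 35. That figure includes subjects kept in follow-up by 6.4.1 and subjects who refuse further contact, and the documents do not give the split. The affected number is smaller and cannot be derived.

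**The case against.** The strongest reply is that nothing here is a contradiction. No text ends AE collection at the EW visit, 8.1.4 and 8.1.2 bind the site for every subject, and a site can make the discharge entry and still telephone on day 28. Footnote b itself expects some contact after the EW visit, and the investigator who decides on those visits is the person bound by 8.1.4. This stands, and it limits the point: the duty exists, but the withdrawal procedure does not implement it and, followed literally, works against it.

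Second, many safety withdrawals carry mandated further contact under 6.4, 7.7 and 8.1.4.1, and a subject seen for one reason would be asked about others. This stands in part. A reader might infer that subjects withdrawn for toxicity are simply lost to AE collection. The documents do not support that, because follow-up of the known event is required. It may end before day 28, however, so the gap is narrowed and not closed. Text after 7.6.2 is blacked out, so any kidney-injury follow-up set there cannot be judged.

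Third, the consequence is modest. SAEs that come to the investigator's attention are still reported, safety summaries are mainly descriptive, and SAP 3.6.1 ties treatment emergence to an effective duration of treatment with no stated lag. It is therefore not shown that late non-serious events would enter the treatment-emergent tables. This also stands.

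Fourth, a reader might infer from the 24-to-32-day range that the completers' schedule is defective too. It is not: day 28 always falls inside the existing Visit 10 window, so compliance is a matter of booking.

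**Conclusion.** The concern holds for subjects withdrawn from the study who still consent to contact. For them the visible text requires active elicitation to at least day 28 but schedules none after the EW visit. The uncovered time is 28 days less the lag from last dose to EW visit. It approaches 28 days only when that visit falls at or just after the last dose.

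Two larger readings are not supported. One is that some 32 to 35 subjects each lose 28 days of AE collection: that range is a planning figure for everyone not completing dosing, and neither the affected number nor the EW timing is given. The other is that the comparison of AE rates between arms is biased: this would need withdrawal, and missed events, to differ by arm, and the documents give no basis for a size. The primary endpoint is unaffected.

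The conclusion rests on the unredacted text and on reading 6.4.1 as governing those who only stop treatment. The change should be made because the omission concerns a stated safety duty and is cheap to repair.

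**What to change.** In Protocol 6.4 and in footnote b of the Schedule of Activities:

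- Keep the IRT entry at the EW visit as it is, so that discontinuation is registered without delay.
- Add a required AE/SAE contact at 28 days or more after the last dose for every withdrawn subject who has not withdrawn consent to contact. A telephone call is enough.
- Close AE collection only after that contact. If the subject cannot be reached, document the attempts.

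For completers no new procedure is needed. Sites should book Visit 10 within its present window, on or after 28 days from the actual last dose.

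The cost is a line in each of two places and one telephone call per early withdrawal. Visit windows, Day 1 anchoring and the SAP stay as they are.

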8.1.4.1. Reporting SAEs to Pfizer Safety

All SAEs occurring in a subject during the active collection period are reported to Pfizer Safety on the CT SAE Report Form.

SAEs occurring in a subject after the active collection period has ended are reported to Pfizer Safety if the investigator becomes aware of them; at a minimum, all SAEs that the investigator believes have at least a reasonable possibility of being related to investigational product must be reported to Pfizer Safety.

Follow up by the investigator continues throughout and after the active collection period and until the event or its sequelae resolve or stabilize at a level acceptable to the investigator, and Pfizer concurs with that assessment.

8.1.4.2. Recording Non-serious AEs and SAEs on the CRF

During the active collection period, both non-serious AEs and SAEs are recorded on the CRF.

Follow-up by the investigator may be required until the event or its sequelae resolve or stabilize at a level acceptable to the investigator, and Pfizer concurs with that assessment.

8.1.5. Causality Assessment

The investigator's assessment of causality must be provided for all AEs (serious and non-serious); the investigator must record the causal relationship on the CRF, and report such an assessment in accordance with the SAE reporting requirements, if applicable. An investigator's causality assessment is the determination of whether there exists a reasonable possibility that the investigational product caused or contributed to an AE; generally the facts (evidence) or arguments to suggest a causal relationship should be provided. If the investigator does not know whether or not the investigational product caused the event, then the event will be handled as "related to investigational product" for reporting purposes, as defined by the sponsor. If the investigator's causality assessment is "unknown but not related" to investigational product, this should be clearly documented on study records.

In addition, if the investigator determines that an SAE is associated with study procedures, the investigator must record this causal relationship in the source documents and CRF, and report such an assessment in the dedicated section of the CT SAE Report Form and in accordance with the SAE reporting requirements.

8.1.6. Sponsor's Reporting Requirements to Regulatory Authorities

AE reporting, including suspected unexpected serious adverse reactions, will be carried out in accordance with applicable local regulations.

8.2. Definitions

8.2.1. Adverse Events

An AE is any untoward medical occurrence in a study subject administered a product or medical device; the event need not necessarily have a causal relationship with the treatment or usage. Examples of AEs include, but are not limited to:

- Abnormal test findings;
- Clinically significant signs and symptoms;
- Changes in physical examination findings;
- Hypersensitivity;
- Progression/worsening of underlying disease;
- Drug abuse;
- Drug dependency.

Additionally, AEs may include signs and symptoms resulting from:

- Drug overdose;
- Drug withdrawal;
- Drug misuse;
- Drug interactions;
- Extravasation;
- Exposure during pregnancy (EDP);
- Exposure via breastfeeding;
- Medication error;
- Occupational exposure.

